1.2.5.2. Immunology Parameters

A secondary immunology endpoint is the flow cytometry response magnitude from the Lytic Granule Loading assay at baseline and Week 15 visits. The Lytic Granule Loading assay may examine the following external cellular markers: CD3, CD4, CD8 (T cell identification), CD137, CD38, and CD69 (T cell activation markers) as well as PD-1 (exhaustion/activation marker).

Exploratory immunology endpoints include the following:

- Levels of serum anti-HPV-16 and anti-HPV-18 antibody concentrations at baseline and Weeks 15, 36, and 88 visits
- Interferon- γ ELISpot response (spot forming units [SFU]) at baseline and Weeks 15, 36, and 88 visits.
- Proinflammatory and immunosuppressive elements results including, but not limited to, CD8+ and FoxP3+ infiltrating cells as well as Granulysin, Perforin, CD137, CD103 and PD-L1 in intra-anal and/or peri-anal tissue as sample allows.

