1.1.5.2. Secondary Objectives

The secondary objectives include the following:

- To evaluate the safety and tolerability of VGX-3100 delivered IM followed by EP
- To determine the efficacy of 3 doses of VGX-3100 as measured by histologic regression of anal or anal/peri-anal HSIL
- To determine the efficacy of 3 doses of VGX-3100 as measured by virologic clearance of HPV-16 and/or HPV-18 by testing from lesion tissue
- To determine the efficacy of 3 doses VGX-3100 as measured by virologic clearance of HPV-16 and/or HPV-18 by intra-anal swab testing
- To determine the efficacy of 3 doses of VGX-3100 as measured by complete histopathologic regression of anal or anal/peri-anal HSIL to normal tissue
- To determine the efficacy of 3 doses of VGX-3100 as measured by histopathologic non-progression of anal or anal/peri-anal HSIL
- To describe the efficacy of VGX-3100 for partial responders, as measured by reduction in the number of intra-anal and/or peri-anal lesion(s), as applicable and the reduction in the size of peri-anal qualifying lesion(s), if present, and for whom the disease has not progressed according to Investigator judgment in subjects who did not have anal or anal/peri-anal HSIL lesion resolution at Week 36
- To determine the cellular immune response following administration of VGX-3100 at post dose 3, and after additional dosing compared to baseline

- To determine the efficacy of 3 doses of VGX-3100 with respect to histopathologic regression of anal or anal/peri-anal HSIL or virologic clearance of HPV-16 and/or HPV-18

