1.1.5.3. Exploratory Objectives

The exploratory objectives include the following:

- To describe the long-term efficacy of VGX-3100 with respect to combined histopathologic regression of anal or anal/peri-anal HSIL and virologic clearance of HPV-16 and/or HPV-18
- To describe the long-term efficacy of VGX-3100, as measured by histologic regression of anal or anal/peri-anal HSIL
- To describe the long-term efficacy of VGX-3100, as measured by virologic clearance of HPV-16 and/or HPV-18 by testing from lesion tissue
- To describe the long-term efficacy of VGX-3100, as measured by virologic clearance of HPV-16 and/or HPV-18 by intra-anal swab testing
- To evaluate tissue immune responses to VGX-3100 in intra-anal and/or peri-anal samples
- To describe the clearance of HPV-16 and/or HPV-18 infection from non-anal anatomic locations
- To describe the association of microRNA (miRNA) profile, previous anoscopy, cytology, and HPV testing results with Week 36 histologic regression
- To describe the patient reported outcomes (PRO) for subjects treated with VGX-3100
- To determine the humoral and cellular immune response following administration of VGX-3100 at post dose 3, and after additional dosing compared to baseline
- To determine the long-term efficacy of VGX-3100 with respect to histopathologic regression of anal or anal/peri-anal HSIL or virologic clearance of HPV-16 and/or HPV-18

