1.2. Study Design

1.2.1. Synopsis of Study Design

HPV-203 is a Phase 2, open-label efficacy study of VGX-3100 (DNA plasmids encoding E6 and E7 proteins of HPV types 16 and 18) administered by IM injection followed by EP in adult men and women who are HIV negative with histologically confirmed anal or anal/peri-anal

HSIL associated with HPV-16 and/or HPV-18. Approximately 24 subjects will receive at least 3 doses of VGX-3100. Each dose of VGX-3100 will be administered IM in a 1-mL volume followed immediately by EP.

To be eligible for the study, subjects must consent to participate and agree to the collection of anal lesion tissue samples for anal cytology and genotyping, a Digital Anal Rectal Examination (DARE), blood samples for immunologic assessments, high-resolution anoscopy (HRA) and HRA-guided biopsies. All intra-anal and/or peri-anal lesion(s) of adequate size ($\geq 4\text{mm}$) will be biopsied at Screening. Biopsy slides will be sent to a Pathology Adjudication Committee (PAC) for evaluation before enrollment. To be eligible for enrollment, the PAC must assign the diagnosis of anal or anal/peri-anal HSIL (AIN2, AIN3, PAIN2, PAIN3) based on the biopsy sample(s). Subjects must also have intra-anal and/or peri-anal lesion tissue test positive for HPV genotype 16 and/or 18 to be eligible for participation in the study.

Depending upon their disposition with regard to histologic and lesion area changes during the trial, all eligible subjects who consent to participate in the HPV-203 study will receive at least three doses of VGX-3100 (6 mg in 1 mL) administered IM (deltoid, preferred site, or anterolateral quadriceps, alternate site), each followed immediately by EP with the CELLECTRA™ 5PSP device. The first study treatment will be administered on Day 0, the second at Week 4, and the third at Week 12. Partial response to VGX-3100 may still be of medical importance by being able to limit the extent of surgery necessary. For partial responders at Week 36, a fourth dose may be administered at Week 40.

To assess quality of life and related impacts on subjects, PRO instruments will be provided and will include the Short Form Health Survey version 2 (SF-36v2™), the EQ-5D-5L, and 2 additional PRO questions assessing quality of life after surgery or biopsy.

The total duration of the study is up to 10 weeks for the screening period and up to 88 weeks for the treatment and follow-up periods.

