3.8. Subpopulations

Week 64 and Week 88 exploratory efficacy endpoints will be additionally analyzed according to number of doses received (3 vs 4).

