4.3.4. Immunogenicity Endpoints

The following immunology endpoints will be analyzed:

- ELISpot results will be presented by scheduled visit and increase from baseline will be analyzed using an exact non-parametric 95% CI on the median at each time point after baseline (Weeks 15, 36, and 88).
- HPV-16 and HPV-18 E7-specific ELISA results will be presented by scheduled visit and analyzed using geometric mean titers and t-distribution 95% CI on the geometric mean titer at each time point after baseline (Weeks 15, 36, and 88).
- Increase from baseline in frequency of VGX-3100-specific CD8+/CD137+ peripheral blood mononuclear cells that are Perforin+ will be analyzed using an exact non-parametric 95% CI on the median.

- Change from baseline in proinflammatory and immunosuppressive elements in tissue based on nanostring assays will be analyzed using a t-distribution based 95% CI on the mean.

All immunogenicity data will be presented by study visit in data listings.

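### No planned immunology summary isolates the response after dose 4, although a secondary and an exploratory objective ask for it

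*SAP*

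**What the plan says.** SAP section 1.1.5.2 lists as a secondary objective: "To determine the cellular immune response following administration of VGX-3100 at post dose 3, and after additional dosing compared to baseline". Section 1.1.5.3 repeats both time frames for an exploratory objective that adds antibody response: "To determine the humoral and cellular immune response following administration of VGX-3100 at post dose 3, and after additional dosing compared to baseline".

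The additional dose is defined in section 1.2.1: "For partial responders at Week 36, a fourth dose may be administered at Week 40".

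Section 1.2.5.2 names one secondary immunology endpoint, the size of the flow cytometry response in the "Lytic Granule Loading assay at baseline and Week 15 visits". Antibody levels and ELISpot are exploratory endpoints, measured at baseline and Weeks 15, 36 and 88.

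Section 4.3.4 sets the analyses:
- **ELISpot:** "ELISpot results will be presented by scheduled visit and increase from baseline will be analyzed", with an exact interval for the median at Weeks 15, 36 and 88.
- **ELISA:** a geometric mean titer with a t-based interval at the same three weeks.
- **Flow:** "Increase from baseline in frequency of VGX-3100-specific CD8+/CD137+ peripheral blood mononuclear cells that are Perforin"-positive, with an exact interval for the median and no visit named.

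None of these lines mentions the number of doses received. The general rule on that split is in section 3.8: "Week 64 and Week 88 exploratory efficacy endpoints will be additionally analyzed according to number of doses received", 3 against 4.

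**The concern.** The objectives have two parts: the response after dose 3, and the response after the additional dose. The endpoints and analyses serve the first part well, since Week 15 falls shortly after dose 3. For the second part, the secondary endpoint stops before the dose is given. The one later immunology visit mixes subjects who received dose 4 with subjects who did not.

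If the plan is followed as written, the study report will hold a Week 88 ELISpot median and a Week 88 geometric mean titer that cannot be read as the response after dose 4. Anyone who wants that figure must pick subjects out of listings after the fact. Section 4.3.2 shows that the need to separate the two groups was recognised for efficacy.

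**Working it through.** The plan gives no figure on this point to reproduce, so the check traces objective to endpoint to analysis and then sizes the gap.

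**Timing** (visits from sections 1.2.1, 1.2.5.2 and 4.3.4)
- Dose 3 to the flow visit: 15 − 12 = 3 weeks.
- Flow visit to dose 4: 40 − 15 = 25 weeks. Flow cannot reflect dose 4.
- Dose 4 to the last ELISpot and ELISA visit: 88 − 40 = 48 weeks. Week 88 is the only visit for these assays after dose 4, because Week 36 comes before it.

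**Where the dose split appears**
- Section 3.8 words it for exploratory efficacy endpoints at Weeks 64 and 88.
- Section 4.3.2 repeats it for every binary efficacy endpoint assessed at Week 64 or Week 88.
- Section 4.3.4 does not contain it.
- Section 3.2 makes an overall summary the default.
- Sections 1.2.5.1 and 1.2.5.2 list efficacy and immunology endpoints under separate headings, so the label used in 3.8 most naturally leaves immunology out.

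**Comparison with baseline.** The ELISpot line analyses increase from baseline. The ELISA line gives titers at each visit and no change, although the exploratory objective asks for a comparison with baseline.

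**Size of the mixing.** The SAP gives no expected number of dose-4 subjects, so let k be that number out of 24, an assumed range. The share of pooled Week 88 values from subjects without dose 4 is (24 − k)/24 if all 24 contribute.

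**What a separate summary could deliver.** For m subjects, the widest exact interval for the median runs from the smallest to the largest value and has coverage 1 − 2 × (1/2)^m:
- m = 4: 1 − 2/16 = 87.5%
- m = 5: 1 − 2/32 = 93.75%
- m = 6: 1 − 2/64 = 96.9%

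An exact 95% interval therefore needs at least 6 subjects.

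| k (assumed) | Share without dose 4 | Exact interval for the dose-4 median |
|---|---|---|
| 4 | 20/24 = 83% | none at 95% (maximum 87.5%) |
| 8 | 16/24 = 67% | 1st to 8th value, coverage 1 − 2/256 = 99.2% |
| 12 | 12/24 = 50% | 3rd to 10th value, coverage 1 − 2 × (1 + 12 + 66)/4096 = 96.1% |

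**Attrition.** Section 3.1 assumes 90% evaluable at Week 36, and 24 × 0.9 = 21.6, about 22. If 22 subjects contribute at Week 88 and all k dose-4 subjects are among them, the shares become 18/22 = 82%, 14/22 = 64% and 10/22 = 45%. The picture does not change.

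**The case against.** Several points can fairly be made for the plan.

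- **An analysis after dose 4 exists.** A reader might infer that the plan yields no estimate at all after the additional dose. The SAP does not support that. ELISpot is a cellular assay, its increase from baseline is planned at Week 88, and dose-4 subjects contribute to it. This objection stands and limits the point: what is missing is a summary that separates those subjects.
- **Section 3.8 may reach further.** Section 4.3.4 is numbered under 4.3, which is headed as efficacy, so the rule could be stretched to Week 88 ELISpot and ELISA. The separate endpoint headings make this the less likely reading, and it would not help flow. At most it shows that the wording is open to two readings.
- **Table shells are elsewhere.** Sections 7.1 and 7.2 place the output list and shells in separate documents, which might show split panels. That cannot be checked here. For efficacy, the SAP sets the split in its own text, and the same would be expected for immunology.
- **Nothing is lost.** Sections 4.3.4 and 4.4.1 list immunogenicity and dosing data by subject, so the dose-4 subjects can be found. That is true, but a listing is not a planned estimate.
- **Only description is at stake.** Section 3.2 reserves formal testing for the primary endpoint. This limits the severity but does not answer the objective.

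**Conclusion.** The point holds in a limited form. The secondary flow endpoint ends 25 weeks before dose 4. The one ELISpot and ELISA visit after dose 4 is planned without the dose split that efficacy receives, so no planned summary isolates the response after dose 4. Under assumed uptake of 4, 8 or 12 of 24, between 83% and 50% of the pooled Week 88 values would come from subjects without dose 4. The true share is unknown because the SAP does not state the expected uptake.

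A separate summary also has limits. Week 88 shows the response 48 weeks after dose 4, not an early or peak response. Dose-4 subjects are selected as partial responders, so a difference between the 3-dose and 4-dose groups cannot be read as the effect of dose 4.

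The consequence is moderate. Part of one secondary and one exploratory objective goes unanswered; the primary test is not touched and no data are lost.

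**What to change.** 1. In sections 3.8 and 4.3.4, extend the 3 versus 4 dose split to Week 88 ELISpot and ELISA.
2. For dose-4 subjects, report within-subject change from baseline, which is what the objectives ask for. Add change from Week 36, the last immunology visit before dose 4, as a supplement. For ELISA, express both as geometric mean ratios with t-based intervals.
3. If fewer than 6 subjects received dose 4, show individual ELISpot and ELISA values, because an exact 95% interval for the median does not then exist.
4. In section 1.2.5.2, state that flow does not address the response after the additional dose, that Week 88 reflects the response 48 weeks after dose 4, and that 3 versus 4 dose comparisons are descriptive because dose-4 subjects are selected on their Week 36 response.

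The cost is SAP wording and a few extra table panels. No new samples are needed, since Weeks 36 and 88 are already planned for both assays. The downside is a small subgroup whose intervals may be wide or, for the median, unavailable.

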1.2.5.3. Safety Parameters

Safety evaluations performed during the study included physical examinations, measurement of vital signs, 12-lead ECGs, clinical laboratory evaluations including hematology, serum chemistry, and CPK, and monitoring of AEs, including injection site reactions.

The secondary safety endpoints are:

- Local and systemic events for 7 days after each dose as noted in the Participant Diary Card
- All AEs including SAEs, unanticipated (serious) adverse device effect, and other unexpected AEs for the duration of the study (through the Week 88 visit)

2. SUBJECT POPULATION

2.1. Population Definitions

The following subject populations will be evaluated and used for presentation and analysis of the data:

- Modified Intention-to-Treat (mITT) Population: All subjects who receive at least 1 dose of VGX-3100 + EP.
- Per-protocol (PP) Population: All subjects who receive all doses of VGX-3100 + EP and have no protocol violations. Subjects excluded from the PP population will be identified and documented before locking of the study database.
- Safety Population: All subjects who receive at least 1 dose of VGX-3100 + EP.

The mITT population is the primary population for the analysis of efficacy parameters. The PP population will be considered supportive of the corresponding mITT population for the analysis of efficacy. The Safety population is the primary population for the analysis of safety endpoints.

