VGX-3100 contains plasmids that target HPV-16 E6/E7 and HPV-18 E6/E7 antigens. The plasmids were designed and constructed using proprietary synthetic vaccine (SynConTM) technology. This process involves synthetically deriving consensus genes across multiple strains and optimizing DNA inserts at the genetic level to allow high expression in human cells. Together, VGX-3100 and the CELLECTRATM device represent an integrated Investigational Product (IP) designed as a non-surgical treatment of HPV-16/18-related anal or anal/peri-anal high grade squamous intraepithelial lesion (HSIL; AIN2, AIN3, PAIN2, and PAIN3) via an immune response directed against HPV-16/18.

A total dose of 6 mg VGX-3100 DNA has been selected for this study based on previous human experience with VGX-3100, preclinical data with VGX-3100 and other DNA vaccines, and the safety and immunogenicity data generated in the HPV-001, HPV-003, and HPV- 101 studies. In the HPV-001 trial, the 6 mg dose was delivered IM followed by EP, which showed trends toward higher response rates and magnitudes of interferon- γ (IFN- γ) enzyme-linked immunospot assay (ELISpot) responses compared with the low (0.6 mg) and mid-dose (2 mg) cohorts without significant safety issues.

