4.4. Safety Analyses

Safety analyses will be conducted using the Safety population.

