4.4.1. Study Drug Exposure

Study drug exposure will be tabulated by the number of doses received. The number and percentage of subjects will be reported.

Compliance will be measured by the following parameters: success of EP, the location of the EP treatment, the size of EP array, and whether or not a guide was used.

Dosing information for each subject will be presented in a data listing.

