4.4.2. Adverse Events

All AEs will be coded using the most current version of the MedDRA coding system and displayed in tables and data listings using system organ class (SOC) and preferred term.

Analyses of AEs will be performed for those events that are considered treatment-emergent, where treatment-emergent is defined per protocol as any AE with onset after the administration of study medication through the end of the study (i.e., study discharge).

An AESI is defined as an AE deemed related to VGX-3100 delivered with CELLECTRA™ 5PSP that requires expedited communication from the site to the Sponsor and meets any of the following criteria per the Toxicity Grade for Healthy Adults:

- Grade 3 or greater persistent administration site erythema, and/or induration recorded ≥ 2 hours immediately after study treatment
- Grade 4 or greater persistent administration site pain, tenderness recorded ≥ 2 hours immediately after study treatment
- Grade 3 or greater fewer
- Grade 3 or greater systemic symptoms, including generalized pruritus

Separate summaries of AEs will be presented for events with an onset within the first 7 and 28 days after injection and overall. The summary will include the number and percentage of subjects with any treatment-emergent AE (TEAE), any TEAE assessed by the Investigator as related to treatment, any AESI, any TEAE by Common Terminology Criteria for Adverse Events (CTCAE v4.03) grade, any SAE, any pre-treatment AE, any AE leading to discontinuation of treatment, and any AE leading to death.

In these tabulations, each subject will contribute only once (i.e., the most related occurrence or the most intense occurrence) to each of the incidences in the analysis, regardless of the number of episodes. In addition to the number of subjects that experienced at least 1 of the events, the total number of events observed across subjects will also be reported.

Summary tables by SOC and preferred term will be produced for the following:

- All TEAEs
- All TEAEs by most recent injection
- All TEAEs by severity grade
- All TEAE assessed as at least possibly related to treatment by the Investigator (i.e., treatment-related)
- All TEAEs with onset within 7 days of an injection
- All TEAEs with onset within 7 days by severity grade
- All treatment-related TEAEs with onset within 7 days of an injection
- All TEAEs with onset within 28 days of an injection
- All TEAEs with onset within 28 days of an injection by severity grade

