- All treatment-related TEAEs with onset within 28 days of an injection

For each tabulation, TEAEs are summarized by proportions of subjects; therefore, in any tabulation, a subject contributes only once to the count for a given TEAE (SOC or preferred term), irrespective of the number of episodes of a particular AE term reported. Injection site reactions are included in the TEAE summaries. The frequency of subjects with preferred term events with onset within 7 days and, separately, within 28 days after dosing will be summarized with percentages and exact Clopper-Pearson 95% CIs.

All AEs occurring on-study will be listed in subject data listings. By-subject listings also will be provided for the following: AEs leading to death, SAEs, AEs with severity \geq Grade 3, AEs leading to discontinuation of treatment, and AESIs.

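### The Safety Population requires EP as well as injection, so a subject injected with VGX-3100 who never receives EP is left out of the safety summary tables

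*SAP*

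**What the plan says.** SAP section 2.1 gives two sets the same entry condition:

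- "Safety Population: All subjects who receive at least 1 dose of VGX-3100 + EP"
- "Modified Intention-to-Treat (mITT) Population: All subjects who receive at least 1 dose of VGX-3100 + EP"

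No wider set, such as all injected subjects, is defined. Section 4.4 then states: "Safety analyses will be conducted using the Safety population".

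The synopsis in section 1.2.1 describes a dose as two steps in sequence: "Each dose of VGX-3100 will be administered IM in a 1-mL volume followed immediately by EP". Section 4.4.1 treats the outcome of the second step as something to be recorded: "Compliance will be measured by the following parameters: success of EP, the location of the EP treatment, the size of EP array". Section 4.4.2 starts treatment emergence at dosing without naming EP: "any AE with onset after the administration of study medication through the end of the study". The same section also provides that "All AEs occurring on-study will be listed in subject data listings".

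**The concern.** Entry to a safety set should follow from exposure. Here it also depends on a procedure that comes after the exposure and whose tolerability is part of a secondary objective (section 1.1.5.2). A subject could be injected, receive no EP, and never return for a dose with EP. That subject has been exposed to the DNA product, and any event after the injection can meet the treatment-emergent definition. Under the literal wording of section 2.1, however, the subject is in neither the numerator nor the denominator of the adverse event tables.

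The second difficulty is that the SAP gives no rule for EP that is attempted, partial or unsuccessful. Whether such a subject belongs to the Safety Population would have to be settled case by case, in an open-label trial. At stake are the counts and percentages in the safety summaries of a study with 24 planned subjects, where a single subject is visible in every percentage.

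**Working it through.** **Plan's own figure.** The SAP gives no figure for this point: no EP failure rate and no expected size of the Safety Population. Its one design figure, about 80% power in section 3.1, is not affected, because the mITT set stays as it is. For completeness, 24 × 0.90 = 21.6 evaluable. The exact one-sided 0.05 binomial test of 0.15 against 0.40 has power 0.800 with 21 subjects and 0.842 with 22 (reject at 7 or more responders in both cases).

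**Reading the sections together.**

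| Situation for a subject | Safety Population under section 2.1 |
|---|---|
| At least one dose given with EP | In |
| Injected, no EP at any dose | Out, read literally |
| Injected, EP attempted, partial or failed at every dose given | Not stated |
| Injected without EP at dose 1, later dose given with EP | In |

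Only the second row is an exclusion that follows from the text. The third row is an ambiguity. In the second row, section 4.4.2 can still classify an event as treatment-emergent, so the event definition and the analysis set do not match.

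**Size, as an illustration.** Input: 24 subjects (section 3.1). Assumption, not in the documents: k of 24 injected subjects never receive EP.

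- Share of exposed subjects missing from the tables = k/24: 0% for k = 0, 4.2% for k = 1, 8.3% for k = 2.

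Take k = 1, and let x of the other 23 subjects have a given event. The table shows x/23.

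- If the omitted subject also had the event, the figure over all exposed is (x + 1)/24.
  - x = 0: 0/23 = 0% instead of 1/24 = 4.2%.
  - x = 7: 7/23 = 30.4% instead of 8/24 = 33.3%.
- If the omitted subject did not have the event, the figure over all exposed is x/24.
  - x = 7: 7/23 = 30.4% instead of 7/24 = 29.2%.

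Clopper-Pearson 95% limits for the case x = 0:

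- 0/23: upper limit = 1 − 0.025^(1/23) = 0.148, so 0 to 14.8%.
- 1/24: lower limit = 0.025 quantile of Beta(1, 24) = 0.001; upper limit = 0.975 quantile of Beta(2, 23) = 0.211, so 0.1% to 21.1%.

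The omission therefore lowers the reported rate if the missing subject had the event and raises it slightly if not.

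**The case against.** The strongest reply is that the wording names the product and sets no completion test. Section 1.1.1 presents the drug and the device as one integrated investigational product, and section 1.2.1 has every dose followed at once by EP. Section 2.1 does not ask for successful or completed EP. Section 4.4.1 lies within the safety analyses, which suggests that unsuccessful EP is to be reported inside the Safety Population and is not a ground for leaving it. This stands in part: a reader might infer that every subject whose EP fails or is interrupted is excluded, and the text does not support that. It does not settle the matter, because the SAP nowhere says that the phrase is shorthand or that an attempted EP counts.

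The second reply is that nothing would be hidden. Section 4.4.2 lists all on-study adverse events by subject, with separate listings for serious events, deaths, events of Grade 3 or higher, events leading to discontinuation of treatment, and events of special interest. Section 4.1 reports the number treated and the number in each population, so a gap would show. The stopping rules in section 1.2.3 refer to subjects and events, not to the Safety Population. All of this stands. A reader might infer that such a subject disappears from the safety reporting altogether; the loss is from the summary tables only.

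Third, the size is hypothetical, and the two intervals above overlap widely. This also stands. A reader might infer a demonstrated bias in favour of the product, since those who cannot tolerate the procedure seem the likeliest to go without EP. That is plausible, but the SAP does not document it, and the arithmetic allows either direction. The point is also weaker for events of special interest, which section 4.4.2 defines by relation to the drug as delivered with the device.

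**Conclusion.** The point holds in a narrow form. As written, a subject with an injection but no EP at any dose is outside the safety summary tables although exposed, and the status of attempted, partial or failed EP is undefined. The number of such subjects is unknown and may be zero. Each would be about 4.2 percentage points of a 24-subject trial. The contrast of 0/23 with 1/24 rests on two assumptions: that one such subject occurs, and that this subject has the only case of the event. No efficacy result and no power figure is affected. The expected effect is small, but the definition belongs to the SAP and is easily put right before database lock.

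**What to change.** In section 2.1, define the Safety Population as all subjects who receive any VGX-3100 injection, in whole or in part, regardless of whether EP was applied or completed. This also removes the question of how attempted, partial or failed EP counts towards the safety set. Keep EP success in the exposure and compliance summary of section 4.4.1, so that the tables show how many doses were given without successful EP. Leave the mITT definition unchanged.

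The cost is one sentence in the SAP. No new data are needed, the sample size and power are unaffected, and if no such subject occurs the tables are identical.
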